### D. Description, Risks and Justification of Procedures and Data Collection Tools:

Veteran data will be managed and stored on VINCI RedCap and VA server. Non-Veteran data will be collected and managed using REDCap (Research Electronic Data Capture). Study data will be collected and managed using REDCap (Research Electronic Data Capture). REDCap is a secure web application designed to support data capture for research studies, providing user-friendly web-based case report forms, real-time data entry validation (e.g. for data types and range checks), audit trails and a de-identified data export mechanism to common statistical packages (SPSS, SAS, Stata, R/S-Plus). The system was developed by a multi-institutional consortium which includes University of Colorado–Denver and was initiated at Vanderbilt University. The database is hosted at the University of Colorado–Denver Development and Informatics Service Center (DISC), which will be used as a central location for data processing and management. REDCap data collection projects rely on a thorough study-specific data dictionary defined in an iterative self-documenting process by all members of the research team with planning assistance from the DISC. This iterative development and testing process results in a well-planned data collection strategy for individual studies. REDCap also includes a powerful tool for building and managing online surveys. The research team can create and design surveys in a web browser and engage potential respondents using a variety of notification methods. REDCap is flexible enough to be used for a variety of types of research and provides an intuitive user interface for database and survey design and data entry.

Patients in either training period may experience muscle soreness after the first few sessions. The soreness typically does not last more than 2-3 days and does not damage the muscle. The physical therapist will instruct the patient on the proper use of superficial heat or ice if muscle soreness occurs. A minimal risk for falls exists for patients receiving either intervention strategy (pre-PMC or post-PMC). This minimal risk is no different than the risk that is normally present during rehabilitation interventions or walking/moving around with assistance in the SNF.

The outcome measures specified are used in a variety of rehabilitation settings under current reporting and standard of care practices. Furthermore, some physical therapists already use the treatment principles included in the PMC intervention. Therefore, these treatment options are already implemented safely in some settings. Yet without concrete evidence to support the effectiveness of the PMC approach, it is not possible to change the standard of practice on a larger scale to improve the quality of care in this patient population.

#### **E. Potential Scientific Problems:**

There are some limitations that will need to be addressed in future studies. There are a large number of therapists treating patients, but we have methods in place for training to ensure ongoing procedural reliability across sites as a larger number of therapists/sites increases the generalizability of the results. We also acknowledge the heterogeneity in the patient population. While this could dilute the effect of the intervention, we will be then able to determine if the intervention is effective in a wide variety of patients or perhaps more effective in an identified sub-group. This will help guide therapists in future treatment plans.

#### **F. Data Analysis Plan:**

##### Analysis

[figure not shown]
**Primary and Secondary Outcomes:** **The primary outcome (Aim 1) for this study is the change in gait speed between admission and discharge from a SNF. The change in gait speed will be pooled across the six facilities for the two respective time periods (pre and post PMC training).** The mean **change in gait speed** for the independent group of patients tested during the pre-PMC training period will be assessed and compared to the mean change in gait speed for the independent group of patients during the post-PMC training period.

Secondary outcomes include physical function measures (SPPB, TUG) and health care utilization outcomes (emergency room visits, falls, skilled nursing home length of stay, and re-hospitalizations), which will be recorded weekly and at discharge from SNF. Preliminary descriptive and graphical analyses (including boxplots, scatterplots, profile plots to examine change over time) will be used for data cleaning and visualization of primary and secondary outcomes.

**Primary Analysis:** The primary analysis will be an intent-to-treat comparison of change in gait speed from SNF admission to discharge between 2 independent groups of patients (pre and post-PMC training groups). Statistical inference regarding the difference between pre and post-PMC training groups will be based on independent sample t-tests. Comparisons will be made on changes in outcome measures (admission to discharge)

within pre/post PMC training groups. Groups of patients will be pooled from all facilities to form 2 independent samples for comparison of time periods (pre and post PMC training) (See Figure 3). The conclusion about the statistical significance of differences between pre/post groups will be determined by this single statistical test to protect against an elevated risk of false positive conclusions.

**Figure 3.** Data analysis plan

**Secondary Analyses (Aim 2):** We will estimate health care utilization outcomes rates (falls, emergency department visits, skilled nursing home length of stay or re-hospitalizations) for each pre/post PMC training period and compare rates between arms using a likelihood ratio test.

The characteristics of the time trajectory (weekly and at discharge from SNF) for treatment effects will also be analyzed in secondary analyses to inform the development of methods to improve long-term outcomes. The analytic methods will include maximum likelihood estimates from a repeated measures model of the mean effect of gait speed at each of the measurement times. The trend in means will be evaluated using a linear contrast as the summary measure of greatest interest. This approach will evaluate whether there are differences in the first-order trends (slope) between the pre/post PMC training groups. The evaluation of the time trajectory will be conditioned on the stratification variables and the baseline value of gait speed.

The qualitative study will be conducted after quantitative data collection for the parent study has been completed to better understand the process of implementation for future refinement of the program. The audio from the focus group discussions will be transcribed either by two study team members or by Transcription Outsourcing. Two coders will review the transcription and develop a code book in an iterative process until both coders reach agreement. Coded transcripts will be analyzed to identify barriers and facilitators to implementation of PMC.

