### C. Study Design and Research Methods

This study is a preliminary investigation using a pre-post training design in six SNFs (Figure 1). We will pool the data across the six SNFs into the pre and post-PMC training periods to dilute the effect of facility variability. Given that the average length of stay in a SNF is 21 days, the pre/post PMC training design will consist of two independent samples of patients to include only those that were admitted and discharged within a given period. As we get interest from additional facilities, we may submit an addendum to include them. Additional sites would help inform sample size estimates for a potential future, cluster-randomization study design. During the 5-month pre-PMC training period, the rehabilitation therapists will treat patients per the current standard of care and a trained CNA (blinded) or PT/PTA (as necessary) will collect outcomes data at admission, weekly, and at discharge. Then, training on the PMC intervention will occur over a 2-month period. Any patients admitted or discharged in the SNF during the PMC training period will not be used. During the 5-month post-PMC training period, therapists will implement the PMC protocol and collect outcomes data as indicated previously (Figure 1).

The medical records will provide information on prior level of function, age, other medical conditions, **re-hospitalization** and **emergency room visits**, medications, sex, admitting diagnosis, **falls**, SNF length of stay, **discharge location**, evaluation and treatment documentation.

Five focus group discussions of 4-6 therapists each will follow an interview guide and last a duration of approximately 1 hour. Therapist participation is voluntary, and all participants will be asked for informed consent. Discussions will be recorded and transcribed for content analysis.

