### Sample Size Estimates

Statistical power was estimated based on the results of a home-health pilot study of 22 participants: 10 were randomized to PMC, 12 to the usual care interventions. The home health population is similar to the SNF population given both experienced a recent acute hospitalization and subsequent decline in function. However, we anticipate patients in SNF will have less gain in gait speed compared to home health participants because the significant decline in function demonstrated in the patients in SNFs has rendered them unable to manage in the home. Therefore, we used the following results for the power analysis: means  $\pm$  standard deviations (SD) of  $0.31 \pm 0.29$  feet for PMC and  $0.13 \pm 0.12$  for usual care. For the power analysis we used a SD of 0.29 and mean difference of 0.14, which is the midpoint between 0.1 (clinically significant difference) and 0.18 (the difference

of the means of from the home health study). Thus, a sample size of 184 patients completing the study (92/group) will provide 90% power (**assuming the same SD in both groups to be conservative**) to detect differences at least that great. This estimate is conditional upon using a 1-sided, alpha = 0.05 level 2-group t-test.

. Of the sites currently listed under COMIRB 14-2388, we have not begun collecting data at Powerback Rehabilitation. Powerback is a growing facility that, on average, provides rehabilitation services to 120 patients a day. Approximately 2/3 of patients will likely be appropriate for the intervention; thus, across a 10-month data collection phase, we will require an increase in enrollment numbers to 800. Our current number approved is 434, so a total of 1,234 is being requested for approval to accommodate the large numbers of patients being seen for rehabilitation at Powerback. While this exceeds our initial sample size estimates, each facility has more variability than we anticipated (e.g., patient population, ratio of PTs to PTAs, rehab coverage on weekend, in house vs contracted rehab services). Therefore, additional facilities are necessary to better determine the variability of patient outcomes across different types of facilities for a future, multi-site pragmatic clinical trial. Furthermore, anticipated funding through the VA requires us to include facilities with Veterans (e.g., Veterans Community Living Center at Fitzsimons).

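### The trajectory model adjusts for stratification variables that the plan never defines, so adjustment for facility is unspecified there, and the primary comparison only pools facilities

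*Combined protocol and SAP*

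**What the plan says.** Under Secondary Analyses in section IV.F (Data Analysis Plan), the weekly and discharge gait speeds are to be analysed by "maximum likelihood estimates from a repeated measures model of the mean effect of gait speed at each of the measurement times". The target is "differences in the first-order trends (slope) between the pre/post PMC training groups". The adjustment set is given in one sentence, which says that the analysis will be "conditioned on the stratification variables and the baseline value of gait speed". This is the only mention of stratification in the readable text.

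The design is described in section IV.C: "This study is a preliminary investigation using a pre-post training design in six SNFs". The handling of facility follows in the same section: "We will pool the data across the six SNFs into the pre and post-PMC training periods to dilute the effect of facility variability". The primary analysis in section IV.F does likewise: "Groups of patients will be pooled from all facilities to form 2 independent samples for comparison of time periods". It compares change in gait speed by an independent-samples t-test with no covariates.

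Under Sample Size Estimates the plan says that "each facility has more variability than we anticipated". It gives as examples the patient population, the ratio of therapists to assistants, weekend coverage, and in-house against contracted services.

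**The concern.** An analyst cannot carry out the adjustment sentence as it stands, because nothing says which variables to enter. The choice would be made at analysis, possibly with results by period in view, and prespecification is meant to prevent that.

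Facility is the variable to ask about first. The plan's own examples of how facilities differ could plausibly affect how fast patients regain walking speed. If the facilities supply different proportions of patients before and after training, and patients recover at different rates in different facilities, part of that difference appears as a period effect. Pooling does not prevent this, because each pooled mean is weighted by whatever mix happened to be enrolled. The same mechanism applies to the unadjusted primary comparison.

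**Working it through.** **1. Is a stratification variable defined?**

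- Sections IV.B and IV.C describe two consecutive patient samples with no randomisation, so there is no stratified allocation to supply one.
- Section IV.A lists patient characteristics under a covariates label, but for describing the population and interpreting results. Facility is not listed, and the list is not tied to the trajectory model.
- Section IV.F names no facility term, fixed or random, in any analysis.

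Only baseline gait speed is specified.

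**2. Is there a figure in the plan to reproduce?** None is given for this model. The only power figure, 92 per group, belongs to the primary t-test. With a difference of 0.14 and SD 0.29 it matches a two-sided 0.05 test (91.1, rounded up to 92) and not the stated one-sided test (74.2, rounded up to 75). That is a separate matter and nothing below depends on it.

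**3. Could the facility mix shift?** One growing facility accounts for 800 of the 1,234 patients requested, which is 65%. No split by period is given, so the following is an assumption. Suppose its 800 divide 300 before and 500 after, and the other 434 divide 217 and 217.

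- Before: 300/517 = 58%.
- After: 500/717 = 70%, a shift of about 12 points.
- The after-period total of 717 exceeds the 602 per period given in section IV.A. If the large facility is held to 602 − 217 = 385, its share is 385/602 = 64% and the shift is about 6 points.

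An equal split gives no shift.

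**4. Bias in the slope difference.** With no true period effect, and one facility compared with the rest:

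spurious slope difference = shift in share × difference in facility slope.

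The documents give no facility slopes, between-facility SD or intraclass correlation, so both inputs are assumed.

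| Shift in share | Slope difference (m/s per week) | Spurious slope difference (m/s per week) | Over 3 weeks (m/s) |
|---|---|---|---|
| 0.10 | 0.01 | 0.001 | 0.003 |
| 0.20 | 0.03 | 0.006 | 0.018 |

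Set against the 0.14 planning difference, for scale only, these are 0.003/0.14 = 2% and 0.018/0.14 = 13%. That difference was chosen for the primary test; the trajectory model has no planning effect of its own.

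**5. Which term removes it?** I used noise-free data with two facility groups, measurements at weeks 0 to 3, a share moving from 50% to 70%, slopes of 0.05 and 0.02 m/s per week, and no period effect.

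| Model | Period-by-time coefficient (m/s per week) |
|---|---|
| No facility term | 0.006 |
| Facility main effect | 0.006 |
| Facility and facility-by-time | 0 |

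A main effect shifts levels and leaves the slope comparison alone.

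For the primary outcome, the same inputs give changes over 3 weeks of 0.15 and 0.06 m/s. The pooled comparison is then off by 0.20 × (0.15 − 0.06) = 0.018 m/s. Adding a facility main effect to a model for change brings this to 0, so no interaction is needed there.

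**The case against.** The strongest reply is that this is a wording gap in a secondary analysis of a study that calls itself preliminary. The plan rests its significance conclusion on the single primary t-test, so no primary inference depends on the phrase. That stands.

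Several stronger readings are tempting and are not supported:

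- **That the trajectory model is unadjusted for facility.** The adjustment set is undefined, and facility may be exactly what was meant. The text supports only that facility adjustment is not specified.
- **That the plan calls facility its largest source of variation.** It says facilities vary more than expected and ranks nothing. Section IV.E separately acknowledges patient heterogeneity.
- **That no stratifier exists anywhere.** Figure 3, captioned as the data analysis plan, is not shown, and one could be named there.
- **That the facility mix will shift.** Staggered starts do not shift it if each facility contributes both periods. Section IV.A gives both 3 and 5 months for the pre-training window. This looks like leftover text, since the introduction says collection was extended from 3 to 5 months, and a shorter window common to all facilities would not by itself change the mix. The growing facility is the plausible route, and no growth rate is given.

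It is also fair to object that changing the primary model goes beyond clarifying one sentence. It is recommended here as an inexpensive improvement that addresses the same weakness, not because the undefined phrase invalidates the t-test.

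**Conclusion.** The point holds in a limited form. The trajectory model refers to variables that the readable text does not define and the design does not generate. Facility adjustment therefore cannot be assumed, and pooling is no substitute for it. The size of any bias cannot be computed from the documents. The 0.003 to 0.018 m/s above rests wholly on the assumed shifts and slope differences, scales in proportion to both, and is zero if the mix is stable or facility slopes are equal. The gap does not alter the planned basis for the significance conclusion. It should still be corrected, because the rule cannot be followed as written and the correction uses data already collected.

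**What to change.** **Trajectory model (section IV.F, Secondary Analyses).** Replace the reference to stratification variables with facility (six levels) and facility-by-time, and keep baseline gait speed. If admission characteristics such as age, sex or primary diagnosis are also wanted, name them.

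**Primary analysis (section IV.F, Primary Analysis).** Estimate the pre/post difference in change in gait speed from a linear model with period, facility and baseline gait speed. Keep the pooled t-test as a sensitivity analysis. Make both changes before outcomes are examined by period.

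**Cost.** Enrolment is by facility and gait speed is measured at admission, so no new data are needed. The primary model gains five facility coefficients and one for baseline. With 184 completers, residual degrees of freedom go from 182 to 182 − 6 = 176. Linear facility-by-time adds five slope coefficients to the five for facility in the trajectory model. Baseline adjustment should add precision, by an amount the documents do not allow to be calculated. The primary analysis becomes slightly less simple, and a facility with patients in only one period would add nothing direct to the period contrast. These terms deal with a change in facility mix; they do not separate the training effect from other changes over calendar time.

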### Sample Size Estimates

Statistical power was estimated based on the results of a home-health pilot study of 22 participants: 10 were randomized to PMC, 12 to the usual care interventions. The home health population is similar to the SNF population given both experienced a recent acute hospitalization and subsequent decline in function. However, we anticipate patients in SNF will have less gain in gait speed compared to home health participants because the significant decline in function demonstrated in the patients in SNFs has rendered them unable to manage in the home. Therefore, we used the following results for the power analysis: means  $\pm$  standard deviations (SD) of  $0.31 \pm 0.29$  feet for PMC and  $0.13 \pm 0.12$  for usual care. For the power analysis we used a SD of 0.29 and mean difference of 0.14, which is the midpoint between 0.1 (clinically significant difference) and 0.18 (the difference

of the means of from the home health study). Thus, a sample size of 184 patients completing the study (92/group) will provide 90% power (**assuming the same SD in both groups to be conservative**) to detect differences at least that great. This estimate is conditional upon using a 1-sided, alpha = 0.05 level 2-group t-test.

. Of the sites currently listed under COMIRB 14-2388, we have not begun collecting data at Powerback Rehabilitation. Powerback is a growing facility that, on average, provides rehabilitation services to 120 patients a day. Approximately 2/3 of patients will likely be appropriate for the intervention; thus, across a 10-month data collection phase, we will require an increase in enrollment numbers to 800. Our current number approved is 434, so a total of 1,234 is being requested for approval to accommodate the large numbers of patients being seen for rehabilitation at Powerback. While this exceeds our initial sample size estimates, each facility has more variability than we anticipated (e.g., patient population, ratio of PTs to PTAs, rehab coverage on weekend, in house vs contracted rehab services). Therefore, additional facilities are necessary to better determine the variability of patient outcomes across different types of facilities for a future, multi-site pragmatic clinical trial. Furthermore, anticipated funding through the VA requires us to include facilities with Veterans (e.g., Veterans Community Living Center at Fitzsimons).

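### The 90% power stated for 92 patients per group is the two-sided 0.05 result; the one-sided 0.05 test named beside it gives 94.7%

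*Combined protocol and SAP*

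**What the plan says.** The power calculation is in section IV.F, under Sample Size Estimates. Its inputs are explicit: "For the power analysis we used a SD of 0.29 and mean difference of 0.14", with a common SD, "assuming the same SD in both groups to be conservative". The result is "a sample size of 184 patients completing the study (92/group) will provide 90% power", and the test is then named: "This estimate is conditional upon using a 1-sided, alpha = 0.05 level 2-group t-test".

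Under Primary Analysis in the same section, the comparison of change in gait speed between the two periods rests on independent-sample t-tests. Of that comparison the plan says: "The conclusion about the statistical significance of differences between pre/post groups will be determined by this single statistical test". No alpha level and no sidedness is given there. Hypothesis 1 in section I is directional, since it expects greater improvement after training, but it does not state how the test will be run.

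On enrolment, the Sample Size Estimates section says: "Our current number approved is 434, so a total of 1,234 is being requested for approval". It acknowledges that this goes beyond the original estimate and gives reasons. Section IV.A (Outcome Measures) ends each data-collection period either at a calendar limit or at 602 patients, which it describes as half the approved number. No power or detectable difference is given for the larger enrolment.

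**The concern.** A power statement links five quantities: difference, SD, sample size, alpha with its sidedness, and power. Any four fix the fifth. Here all five are printed and they do not fit together, so at least one entry is wrong.

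The shortage or surplus of patients is not the main issue. The sentence that fails to reproduce is also the only source for the significance level and sidedness of the primary comparison. An analyst who relies on the words would use one-sided 0.05. One who infers the intended test from the sample size would use two-sided 0.05. A result with a t statistic between about 1.65 and 1.96 in favour of the post-training period would be significant on one reading and not on the other. The plan rests its significance conclusion on one test to limit false positives, so that choice should be settled in writing before the data are analysed.

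A second, smaller gap is that the calculation describes 184 completers, while the study may now collect data on several times that number.

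**Working it through.** **Inputs** (all from Sample Size Estimates): difference 0.14; SD 0.29 in both groups; equal groups; 92 per group; alpha 0.05; stated power 90%. The 92 per group contains no dropout allowance, because the section counts "184 patients completing the study" and gives no dropout rate.

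**Method.** Two-sample t-test with n per group:
- standard error SE = SD × √(2/n)
- noncentrality λ = difference / SE
- degrees of freedom = 2n − 2
- power = probability that a noncentral t with noncentrality λ exceeds the critical value (upper 5% point if one-sided, upper 2.5% point if two-sided)

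**Step 1: the stated sample size under each test.** At n = 92, SE = 0.29 × √(2/92) = 0.0428, λ = 0.14/0.0428 = 3.274, df = 182.

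| Test | Critical t | Power at 92 per group | Smallest n per group for 90% |
|---|---|---|---|
| One-sided 0.05 (as named) | 1.653 | 94.7% | 75 (150 total) |
| Two-sided 0.05 | 1.973 | 90.3% | 92 (184 total) |

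The plan's own pair, 92 and 90%, is reproduced by the two-sided row and not by the one-sided row.

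**Step 2: normal-approximation check.** n per group = 2 × (SD/difference)² × (z for alpha + z for power)².
- One-sided: 2 × (0.29/0.14)² × (1.645 + 1.282)² = 73.5, so 74.
- Two-sided: 2 × (0.29/0.14)² × (1.960 + 1.282)² = 90.2, so 91.

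The one-patient gap from the exact values is the usual t correction. It does not bridge 75 and 92.

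**Step 3: could something else explain 92 with a one-sided 0.05 test?**
- Pilot SDs: using 0.29 and 0.12 unequally, or pooled (0.214), gives one-sided power above 99%.
- Difference: 92 per group would give 90% one-sided power for a difference of 0.126, but the plan uses 0.14.
- SD: it would have to be 0.323, but the plan uses 0.29.
- Dropout: inflating 75 to 92 implies 1 − 75/92 = 18.5% loss, but the 92 are completers.
- One-sided 0.025 does give 92, but that is the two-sided 0.05 criterion for benefit and not the alpha printed.

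**Step 4: the current enrolment.** Suppose the cap of 602 per period is reached, every patient has both admission and discharge gait speed, SD is 0.29 and patients are independent. Then SE = 0.29 × √(2/602) = 0.0167. The difference detectable with 90% power is:
- one-sided 0.05: (1.645 + 1.282) × 0.0167 ≈ 0.049
- two-sided 0.05: (1.960 + 1.282) × 0.0167 ≈ 0.054

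Both are about half of the 0.1 that the same section calls clinically significant.

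**Step 5: the enrolment totals.** 434 + 800 = 1,234, and 1,234/2 = 617. Section IV.A gives 602 as half the approved number, which would imply 1,204.

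**The case against.** The strongest reply is that nothing is lost. The error runs in the safe direction: under the test named, power is higher than stated, so on the plan's inputs the study is not underpowered. Recruitment does not stop at 184 either, since 434 were already approved. That stands, and it limits the point to a contradiction in the text.

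Four stronger readings are tempting, and the documents do not support them.

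- A reader might infer that the decision threshold is undefined. It is stated once, as one-sided 0.05, and agrees with a directional hypothesis. The defect is that it conflicts with its own sample size and is not repeated where the analysis is specified.
- A reader might treat this as a confirmatory test run at an improper error rate. Section IV.C calls the study a preliminary investigation, and a one-sided test is a permissible design choice if stated consistently.
- A reader might conclude that at 602 per period a trivial difference would be declared a success. The plan lets the test decide statistical significance and defines no success criterion. Sensitivity to small differences comes from the large sample, not from the sidedness error.
- A reader might see the larger enrolment as unexplained, or 602 as a fixed target. It is a cap alongside a calendar limit, and the excess is disclosed with reasons: facility variability, planning of a future trial and a funding requirement. Only the updated precision is missing.

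The figures at 602 also treat patients as independent. The plan gives no within-facility correlation. Since facilities are meant to contribute to both periods, stable facility differences largely cancel if contributions are balanced. The relevant quantity is variation in the facility effect between periods, for which the documents offer no value.

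**Conclusion.** The point holds as an internal contradiction. With difference 0.14, common SD 0.29 and 92 completers per group, the named one-sided 0.05 t-test has 94.7% power, 4.7 percentage points above the figure stated. It would need 75 per group for 90%, which is 17 fewer than planned. The two-sided 0.05 test reproduces 92 per group at 90.3%, so a two-sided calculation labelled one-sided is the likely cause, though the documents do not prove which entry is wrong.

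The consequence is not lost power. The only statement of alpha and sidedness for the primary test cannot be trusted as it stands. These results use only the plan's printed inputs and assume independent patients.

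The missing detectable difference is secondary. The values of 0.049 and 0.054 depend on the cap being reached with complete data and no facility-by-period variation. The mismatch between 602 and 617 is a bookkeeping matter.

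**What to change.** 1. In Sample Size Estimates, make the sentence consistent in one of two ways. Either name a two-sided alpha 0.05 test, which leaves 92 per group and 90% correct and is the likely intent, or keep one-sided alpha 0.05 and restate power at 92 per group as about 95%.
2. In Primary Analysis, state the same alpha and sidedness for the t-test on change in gait speed.
3. Add one sentence giving the difference detectable with 90% power at current enrolment, with the assumptions of step 4 spelled out. Any allowance for facility-by-period variation should be labelled an assumption and shown over a range.
4. Reconcile the 602 per period in section IV.A with the 1,234 total in Sample Size Estimates.

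The cost is a few sentences. No sample size, procedure or data collection needs to change.
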